## 2.3 Model Numbers

The Lava LES Kit is available in two product formulations, Lava-18 (nominal viscosity of 18 cSt), and Lava-34 (nominal viscosity of 33 cSt). Lava-18 will travel more distally and penetrate deeper into the vasculature due to its lower viscosity compared to the Lava-34. **Table 1** summarized the model numbers and descriptions of Lava LES Kits.

There are 4 Stock Keeping Units (SKUs) for Lava. There are two SKUs with a viscosity of 33 centistokes, Lava-34, supplied in 2 ml and 6 ml vials. There are two SKUs with a viscosity of 18 centistokes, Lava-18, each supplied in 2 ml and 6 ml vials.

**Table 2. Model Numbers and Descriptions of Lava LES Kits**

SKU	Model Name	Lava Volume (ml)	Lava Viscosity (centistokes, cSt)
[REDACTED]	Lava-34	6	33
[REDACTED]	Lava-34	2	33
[REDACTED]	Lava-18	6	18
[REDACTED]	Lava-18	2	18

The Lava Mixing Kit is available in 2 options; 2 ml and 6 ml. **Table 3** summarized the model numbers and descriptions of Lava Mixing Kits.

**Table 3. Model Numbers and Descriptions of Lava Mixing Kits**

SKU	Model Name	Volume (ml)
[REDACTED]	Lava Mixing Kit - 6 ml	6

[REDACTED]	Lava Mixing Kit - 2 ml	2
------------	------------------------	---

## 2.4 Device Traceability

Lot number will be used to trace devices in the study.

## 2.5 Indication for Use

The proposed indication for use is for embolization of arterial hemorrhage in the peripheral vasculature.

## 2.6 Device Description

The Lava LES consists of the Lava LES Kit and the Lava Mixing Kit.

The Lava LES Kit comprises the following system components contained in a product shelf carton:

[figure not shown]
- A sterile, sealed, serum vial containing Lava
- A sterile, sealed, serum vial containing DMSO
- A sterile, sealed pouch containing DMSO compatible syringes

Lava is an injectable, non-adhesive liquid embolic agent comprised of three ingredients; tantalum, DMSO, and EVOH. The EVOH copolymer dissolved in DMSO and suspended micronized tantalum powder to provide contrast for visualization under fluoroscopy. Lava is first prepared with the Lava Mixing Kit and then delivered to the target anatomy via a DMSO compatible microcatheter. The Lava precipitates into a spongy, coherent mass or cast upon exposure to blood at the targeted location. The DMSO compatible microcatheter is not part of the study device.

The Lava Mixing Kit is used for homogenization of the Lava and is available in two sizes to accommodate the different volumes of the Lava LES Kit. The Lava LES Mixing Kit comprises the following components contained in a product shelf carton:

- A sterile, sealed pouch containing a mixing manifold
- Two sterile, sealed pouches, each containing a single DMSO compatible mixing syringe

The 6 ml and 2 ml configurations of the Lava LES Kit are depicted in **Figure 1**. The mixing manifold component of the Lava Mixing Kit is depicted in **Figure 2**.

[figure not shown]
**Figure 1. Lava™ LES Kit configurations: left panel displays the kit configuration with the 6 cc vial of Lava and right panel displays the kit configuration with the 2 cc vial of Lava**

## 2.7 Method of Use

- The liquid embolic suspension is delivered to the patient through a DMSO compatible microcatheter. The catheter is selectively placed into the target vascular location and primed with DMSO prior to injecting the liquid embolic suspension. The liquid embolic suspension is delivered by controlled injection into the desired vascular location under fluoroscopic visualization. The total volume of liquid embolic suspension injected should not exceed 3.5 mL. The precipitation of the liquid embolic begins immediately upon exiting the distal end of the microcatheter, beginning from the outside of the embolus and proceeding to the center of embolus. Total precipitation occurs within minutes of exposure to blood or other aqueous media. The distance that the embolus travels prior to full precipitation is dependent on several factors, including the injection rate, the flow rate in the target vasculature, and the viscosity of the embolic.

## 3 PRIOR INVESTIGATIONS

While there are many investigations of other embolic agents, devices, and techniques, and while Onyx has been the subject of single center publications, there have been no prior investigations of Lava LES, to date.

**Figure 2. Mixing Manifold component from Lava Mixing Kit.**

## 4 STUDY OBJECTIVE

The objective of this study is to evaluate the safety and effectiveness of Lava LES embolotherapy for the treatment of hemorrhage from peripheral arteries.

Safety will be evaluated by assessing freedom from 30-day MAE, a composite endpoint that includes those complications that occur at the site of catheter insertion, along the pathway for access to the target arteries, and at the site of administration in the target territory or those non-target arterial beds where embolic agent was inadvertently administered. The MAE rate will be compared to the rates reported in the literature after treatment with other modalities currently used to treat peripheral artery hemorrhage.

Effectiveness will be evaluated by assessing the absence of bleeding in the treated target lesion after embolization with the Lava LES, without the need for reintervention through 30 days after the index procedure.

## 5 OUTCOME VARIABLES

### 5.1 Primary Safety Endpoint Definition

The primary safety endpoint is a composite of freedom from 30-day Major Adverse Events (MAEs). MAEs include the following events as adjudicated by an independent Clinical Events Committee (CEC);

1. Ischemia or infarction of the target territory;
2. Non-target embolization;
3. Allergic reactions to Lava;
4. Catheter breakage;
5. Catheter entrapment.

Each MAE element is determined after enrollment; any events that occur prior to the point of enrollment as defined in **Section 6.5**, below, are not included in the primary safety endpoint. The target territory or territories are specified by the Investigator at the time of enrollment; embolization to a non-target territory is defined as unintentional administration of Lava to a vascular bed outside of a target territory. Catheter breakage refers to defects in the luminal continuity of the microcatheter used to deliver Lava, but not to other catheters that may be used in other aspects of the procedure separate from the administration of Lava. Catheter kinks without defects in luminal continuity will not trigger the endpoint. Catheter entrapment, defined as the inability to withdraw the catheter refers to the catheter with which Lava is administered and is defined by the need for endovascular or open surgical procedures to remove the catheter or portions thereof. Retained portions of the catheter trigger the endpoint, irrespective whether additional endovascular or open surgical procedures were performed.

## 5.2 Primary Effectiveness Endpoint Definition

The primary effectiveness endpointa is Clinical Success, defined as absence of bleeding from the target lesion after embolization with the Lava LES, without the need for emergency surgery, re-embolization, or other target lesion reinterventions within 30 days of the index procedure. Absence of bleeding is defined as no BARC Type 3 or greater bleeding occurring after the index procedure, either persistent or recurrent. The ascertainment of persistent or recurrent BARC Type 3 or greater bleeding does not include bleeding that occurred prior to the conclusion of the index procedure.

The primary effectiveness endpoint will be adjudicated by the CEC, relying on information from the source documents and/or the core laboratory findings of absence of bleeding.b Effectiveness relates to the target lesion(s) as defined by the Investigator at the index procedure.

## 5.3 Secondary Endpoints

The following measures will be assessed as secondary endpoints of the study:

1. Technical Success, defined as absence of angiographic evidence of bleeding from the target lesion at the conclusion of the index procedure;
2. Successful delivery of Lava and intact retrieval of the microcatheter;
3. Assessment of each element of the primary safety endpoint (MAE) as an individual component;
4. Symptomatic ischemia in the target territory that does not require intervention;
5. All-cause mortality;
6. Bleeding-related mortality (attributable to bleeding in a target territory);
7. Open surgical conversion for persistent or recurrent bleeding;
8. Device-related serious adverse events;
9. Procedure-related serious adverse events;
10. Access site hematoma (>5cm in longest axis);c
11. Access site false aneurysm;
12. Units of red blood cells transfused after administration of Lava;

a The effectiveness endpoint is lesion-based and not subject-based. Failure of the effectiveness endpoint is triggered by events that are referable to the specific lesion and not to other events referable to another lesion in the same subject. For example, if a subject has two lesions where the first is treated successfully but the other rebleeds and requires emergency surgery, effectiveness would have been achieved in the first lesion but not in the second.

b Core laboratory-determined assessment of bleeding is used for the primary and secondary endpoints. If core laboratory images are unavailable or uninterpretable, the site-reported determinations will be used.

c As measured on a duplex ultrasound study, assessed by the Core Laboratory.

- 13. Duration index procedure, total and after administration of Lava;
- 14. Contrast administered during index procedure;
- 15. Fluoroscopy time during index procedure;
- 16. Length of stay in the intensive care unit after the index procedure;
- 17. Length of hospitalization, total and after the index procedure.

## 6 STUDY METHODOLOGY

This study is a single-arm trial with primary safety and effectiveness endpoints, designed to assess the outcome after Lava LES arterial embolotherapy of hemorrhage from peripheral arterial vessels.

### 6.1 Study Design

The study is a multicenter, prospective, single-arm trial of the Lava LES in patients with peripheral arterial bleeding in need of treatment. Subjects will be enrolled at up to 20 investigational sites in the United States with no more than 25 subjects enrolled at any single site.

### 6.2 Informed Consent

Written, study-specific informed consent will be obtained from each prospective study participant prior to treatment with the Lava LES. The prospective study participant will be counseled that they are free to refuse entry into the study and free to withdraw from the study at any time without prejudice to future treatment. Subjects will be consented for 1 year to allow for the ability to collect additional data, if initial study results indicate a need for additional longer-term information. The Investigator will keep the original Informed Consent Form (ICF) and a copy will be given to the subject.

Written informed consent may be obtained from a patient's legally authorized representative (LAR) in emergency procedures where informed consent cannot be reasonably obtained from the patient for reasons of hemodynamic instability, medications, or other conditions that prevent comprehension and consideration of the benefits and risks of study participation.d Consent from a LAR will be guided by the institutional local policies, state law, and the relevant IRB.

### 6.3 Study Eligibility

Prospective study participants include those that meet the following inclusion and exclusion criteria:

---

d A legally authorized representative is defined in 21 CFR 50.3(l) as "an individual or judicial or other body authorized under applicable law to consent on behalf of a prospective subject to the subject's participation in the procedure(s) involved in the research."

### 6.3.1 Inclusion Criteria

The prospective study participant must meet each of the following criteria to be eligible for inclusion in the study:

1. Age  $\geq 18$  years;
2. Active arterial bleeding in the peripheral vasculature (defined in **Section 6.4**, below), documented on a suitable imaging study;c
3. Subject or subject's LAR is able and authorized provide written informed consent for the procedure and the study;
4. Willing and able to comply with the specified follow-up evaluation schedule;
5. Life expectancy  $>30$  days;
6. No prior embolization in the target territory.

### 6.3.2 Exclusion Criteria

The prospective study participant must not have any of the following exclusion criteria present at the time of eligibility assessment:

1. Pregnancy or breast feeding. A woman who, in the Investigator's opinion, is of child-bearing potential must have a negative pregnancy test within 7 days before the index procedure;
2. Coexisting signs of peritonitis or other active infection;
3. Participation in an investigational study of a new drug, biologic or device that has not reached its primary endpoint at the time of study screening;
4. Uncorrectable coagulopathies such as thrombocytopenia  $<40,000/\mu\text{L}$ , international normalization ratio (INR)  $>2.0$ ;
5. Contraindication to angiography or catheterization, including untreatable allergy to iodinated contrast media;
6. Anatomic arterial unsuitability such that, in the Investigator's opinion, the delivery catheter cannot gain access to the selected position for safe and intended embolization;

c The site of bleeding must be documented either angiographically at the time of the index procedure or, if no bleeding is observed on the diagnostic angiogram, with a suitable imaging study performed within 48 hours of the index procedure that, in the Investigator's opinion, adequately localized bleeding to a territory or territories suitable for embolization. Empiric embolization, defined as embolization in the absence of arteriographic localization of the bleeding vessel at the index procedure angiogram, will be allowed for bleeding from sites other than the lower gastrointestinal tract (small intestine, colon, and rectum).

7. Known allergy or other contraindication to any components of Lava including dimethyl sulfoxide (DMSO);
8. More than 4 Target Lesions will require embolization, in the Investigator's opinion after performance of diagnostic angiography or another suitable imaging study.f

#### **6.4 Peripheral Arterial Hemorrhage**

Subjects will be eligible for enrollment if bleeding is localized within the peripheral arteries, as defined by gastrointestinal hemorrhage (esophagus, stomach, duodenum, small and large intestine), arterial hemorrhage associated with trauma, visceral artery hemorrhage (including splenic, hepatic, adrenal, pancreas, prostate, bladder, and uterus), traumatic musculoskeletal artery hemorrhage, bronchial artery hemorrhage, or iatrogenic arterial hemorrhage.

Patients with hemorrhage from the vessels of the heart, the intracranial vessels, the vertebral or carotid arteries or branches thereof, vessels of the spinal cord, and those with postpartum gynecological hemorrhage will be ineligible for inclusion in the study.

#### **6.5 Point of Enrollment**

An eligible prospective study participant will meet all eligibility criteria and be considered enrolled when the informed consent form has been signed by the prospective study participant, or the participant's LAR, and after successful arterial access has been established to the Target Lesion.

Consented patients in whom an index procedure is performed but the Investigator decides at the time of the index procedure not to use the Lava LES will be considered screen fails.g

#### **6.6 Study Populations**

Consented patients will be evaluated as follows:

##### **6.6.1 Screen Fails**

Patients who are consented but who, for whatever reason, are not enrolled (e.g., they do not meet the eligibility criteria after diagnostic angiography) will be considered screen failures and will be not be followed further. The reason for excluding these subjects from enrollment will be documented in the Electronic Data Capture (EDC) system.

---

f If the Investigator believed at the time of diagnostic imaging that 4 or fewer lesions required embolization but, during the course of treatment it is in the subject's best interest to embolize more than 4 lesions, the additional lesions must be treated with non-study agents/devices. Any complications related to the additionally embolized lesions will be considered procedure-related but not device-related events. Rebleeding documented to be from the additionally embolized lesions will not trigger the primary effectiveness endpoint.

g Provocative angiography may be performed at the Investigator's discretion. Complications from provocative angiography are considered procedure-related but not device-related events.

### 6.6.2 Intention-to-Treat Population

The Intention-to-Treat (ITT) population will include all consented subjects in whom the Lava LES study device entered the vasculature (as defined in **Section 6.5**, above), irrespective of adherence with the entry criteria, treatment received, subsequent withdrawal, or deviation from the Protocol.

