### 8 ASSESSMENTS AND FOLLOW-UP SCHEDULE

Study participants will be screened for study eligibility pre-procedure and final eligibility will be determined at the time of the diagnostic arteriogram at beginning of the index procedure. Enrollment will occur at the point at which the Investigator makes the decision to perform embolotherapy with the study device (Lava LES) in a previously consented patient. The follow-up period will comprise the post-procedure period through hospital discharge and the 30-day period following the index procedure. Assessments are summarized in the Schedule of Assessments (**Table 7**, below).

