## 8.8 Withdrawals and Loss to Follow-Up

m If an in-window telephone visit prompts an in-person visit that, for scheduling reasons, cannot not performed within the 30-day window, no protocol deviation will be reported. Any abnormalities detected at a late 30-day in-person visit will be assigned to the 30-day visit timepoint.

Study participation is completely voluntary, and each subject is free to withdraw from the study at any time. An investigator also has the right to withdraw the subject from the study in the event of reasons concerning the health or well-being of the subject, or in the case of lack of cooperation. Should a subject decide to withdraw for any reason, or should the investigator decide to withdraw the subject, all efforts will be made to complete and report the observations up to the time of withdrawal as thoroughly as possible. A complete, final evaluation at the time of the subject's withdrawal must be made and an explanation given as to why the subject is withdrawing or being withdrawn from the study.

The reason for and date of withdrawal must be recorded on the subject's End of Study eCRF. If the reason for the withdrawal is a device- or procedure-related AE, the event must be reported to the Sponsor and recorded on the eCRF.

If the procedure is aborted, the subject does not need to complete the follow-up assessments, unless the subject is converted to surgical repair. The subject's enrollment roster position will not be made available to other subjects.

If a subject dies during the course of the study, the Sponsor will request an autopsy provided the subject authorized an autopsy in the event of death during the course of the study. Autopsy observations should include documentation of condition of body organs and determination of device and/or procedure relationship to death.

All efforts will be made to retain subjects in order to collect data at the 30-day the follow-up visit. Due diligence in reaching the subject must be made by:

- Two documented telephone contact attempts, emails, or regular postal mail letters; and
- A certified letter

After the above attempts were made, if no response is obtained, the final evaluation of a given subject will be the last visit at which study-related procedures were performed on that subject. The End of Study eCRF page will need to be completed and communication attempts must be documented.

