## **10.2 Reporting of Adverse Events**

---

o The 2-day timeframe refers to 2 business days from the point at which the Investigator makes the determination that the event is a UADE. This timepoint may be after the point at which the Investigator learns of the event itself.

All adverse events, non-serious and serious, that occur during the study must be reported on the Adverse Event eCRF. The report should include, wherever possible, time of onset, severity, duration, outcome, and the Investigator's medical judgment as to the relationship of the adverse event to the study device, procedure, (i.e. not related, possibly related, definitely related, or relationship unknown).p

All SAEs must be reported to the Sponsor or its CRO within 5 business days of the Investigator's knowledge of the event. The event is reported in the electronic data capture system. IRB notification of the adverse event may also be required, depending on the conditions of approval or requirements of the respective committee. Any UADEs must be reported to the Sponsor/CRO within 1 working day from when the Investigator first learns of it.

Non-serious reportable adverse events are to be submitted via the EDC in a timely fashion. Certain reportable events may require adjudication; therefore, supporting documentation must be sent to the Sponsor/CRO upon request.

Events that occur before consenting of the patient are not reported. Adverse events that occur after consenting in patients that are screen fails, in other words, in those for whom the Investigator decides not to treat with the study device (Lava LES) will also not be reported. Adverse events that occur after consenting of the patient in enrolled subjects (i.e. those for whom the Investigator decided to treat with the study device) will not be reported if they occur prior to the start of the index procedure (defined as the beginning of arterial access; see **Section 6.5**, above), but will be reported as procedure-related adverse events if they occur after the start of the index procedure but before Lava is administered into the delivery catheter.

Events related to preexisting conditions are not reported unless there is worsening of the condition after enrollment (or after the start of the index procedure, as specified in the paragraph above).

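### Enrollment has two definitions and ITT a third, and follow-up is waived for aborted procedures, so undelivered Lava attempts fall outside both primary analyses and the effectiveness rate can be flattered.

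*Protocol*

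**What the plan says.** **Enrollment.** Protocol 6.5 enrolls a consented, eligible patient "after successful arterial access has been established to the Target Lesion". Its second paragraph adds that consented patients who undergo an index procedure but for whom "the Investigator decides at the time of the index procedure not to use the Lava LES will be considered screen fails". Protocol 8 sets a different point: "Enrollment will occur at the point at which the Investigator makes the decision to perform embolotherapy with the study device (Lava LES"). Protocol 10.2 follows Section 8 and describes enrolled subjects as "those for whom the Investigator decided to treat with the study device".

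**ITT.** Protocol 6.6.2 reads: "The Intention-to-Treat (ITT) population will include all consented subjects in whom the Lava LES study device entered the vasculature". It refers to 6.5 for the definition and applies whatever treatment was received. SAP 3.3 uses the same device-entry criterion. All safety endpoints are analysed in ITT.

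**Completed Cases.** Protocol 6.6.3 takes ITT subjects who finish 30-day follow-up and adds those who fail the effectiveness endpoint earlier, however short their follow-up. SAP 3.3 takes only those who complete follow-up. The primary effectiveness analysis uses this set.

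**Aborted procedures.** Protocol 8.8: "If the procedure is aborted, the subject does not need to complete the follow-up assessments, unless the subject is converted to surgical repair".

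**Counting rules.** Protocol 5.1 excludes from the safety endpoint "any events that occur prior to the point of enrollment". Protocol 7.7 and SAP 3.4.1 keep any subject with an MAE in the safety denominator; otherwise follow-up to day 23 is needed (the SAP also accepts withdrawal or loss recorded at or after day 23). SAP 3.4.1 does not impute in the primary analyses.

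**The concern.** In a single-arm trial against a fixed goal, the denominator has to be fixed before the outcome of the attempt is known. Here, membership of both analysis sets depends on what happened during the attempt: whether Lava got in, whether the procedure was completed, and whether anyone made contact afterwards. Attempts in which Lava could not be delivered are unlikely to be successes of the device strategy, and they are the ones the text leaves out. If they are more than isolated cases, the effectiveness rate is estimated in a set selected for technical feasibility. The goal it is compared with is a literature average, and the plan does not say that the source studies made the same selection.

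**Working it through.** **1. Follow each kind of case through the text.**

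- *Access gained, decision made for Lava, Lava never enters.* Enrolled under 6.5 (first paragraph) and under 8. Not ITT, so in neither the safety analysis nor Completed Cases. If the decision is reversed during the procedure, 6.5 permits the label screen fail; 6.6.1 then ends follow-up and 10.2 leaves the adverse events unreported.
- *Lava entered, procedure aborted, no MAE, no recorded failure, no contact by day 23.* In ITT, but out of the safety denominator and out of Completed Cases.
- *Lava entered, aborted, effectiveness failure recorded, no surgical conversion, follow-up not completed.* In Completed Cases under Protocol 6.6.3, out under SAP 3.3.
- *Lava entered and an MAE occurred.* In ITT and in the safety analysis, whatever the follow-up.
- *Converted to surgical repair.* Follow-up is still required.

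One borderline case is unresolved. Protocol 2.6 says the microcatheter is not part of the study device, but the DMSO vial belongs to the Lava LES Kit (2.1) and is used to prime the catheter first (2.7). The text does not say whether priming counts as device entry.

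**2. Reproduce the plan's sample size.** Inputs (Protocol 7.9, SAP 3.2): goal 72%, anticipated rate 84%, one-sided exact binomial test, alpha 0.025, power 80%. At n = 101 the smallest r with P(X ≥ r | 101, 0.72) ≤ 0.025 is r = 82 (alpha 0.0227), and P(X ≥ 82 | 101, 0.84) = 81.9%. Then 101 / 0.90 = 112.2, rounded up to 113. Both stated figures, 101 and 113, reproduce.

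**3. Add omitted attempts back as effectiveness failures.** The documents do not give the number k of undelivered or aborted cases. I assume k from 0 to 12 (12 = 113 − 101), one lesion per subject, and every omitted attempt a failure. The test is whether the exact (Clopper-Pearson) one-sided 97.5% lower limit for x/(101 + k) exceeds 72%.

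- Result near the anticipated rate: 85/101 = 84.2%, limit 75.6%, passes. With k = 4, 85/105 has limit 72.1%, passes. With k = 5, 85/106 has limit 71.3%, fails.
- Minimum pass: 82/101 = 81.2%, limit 72.2%. With k = 1, 82/102 has limit 71.4%, fails.

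Over the assumed range:

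| k | Chance of passing with the k failures counted, if 84% of the 101 evaluable lesions are expected to succeed | Chance of a false pass with the k failures dropped, if true success over all attempts is 72% |
|---|---|---|
| 0 | 81.9% | 2.3% |
| 2 | 65.2% | 4.6% |
| 4 | 54.9% | 8.5% |
| 6 | 33.5% | 14.8% |
| 12 | 5.6% | 49.6% |

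The last column uses P(X ≥ 82) with n = 101 and success probability 0.72 × (101 + k)/101; for k = 4 this is 0.7485.

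**4. Check the direction for safety.** Among ITT subjects, only event-free ones can drop out for want of follow-up. Suppose 11 MAEs in 113 subjects: 102/113 = 90.3%, exact lower limit 83.2%, which passes 82%. Drop 12 event-free subjects: 90/101 = 89.1%, limit 81.3%, which fails. This loss works against the device.

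**The case against.** A reader might infer that both primary rates are biased upward. The documents do not support that for safety. Any ITT subject with an MAE is retained, and step 4 shows that losing event-free subjects lowers the rate. Only an MAE in an enrolled subject outside ITT would be lost, and few can arise there: non-target embolization, allergic reaction and entrapment by adherence all require Lava exposure. Breakage of the microcatheter before delivery is the arguable example, because Section 18 speaks of the catheter used to deliver Lava. Nor is the safety window undefined. Protocol 7.2 runs it from enrollment to 30 days; the difficulty is that its starting point has two definitions.

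A reader might also infer that incomplete deliveries leave the analyses as a class. They do not. Once Lava has entered the vasculature the subject is in ITT, and Protocol 6.6.3 keeps documented early failures. Section 18 makes continued bleeding an effectiveness failure.

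Three further arguments favour the plan. First, the screen-fail paragraph of 6.5 brings that section close to the Section 8 rule, so part of the conflict is drafting. Second, the endpoint is worded as success following embolization with Lava, so an analysis of treated lesions is a recognisable choice. Third, SAP 3.4.1 plans imputation and a tipping-point analysis.

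These stand in part. A treated-set analysis is legitimate if it is named as such and the excluded attempts are accounted for; calling it ITT hides the exclusion. The sensitivity analyses may recover ITT cases lacking follow-up, but they do not reach attempts outside ITT.

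**Conclusion.** The conflict between the enrollment points, the ITT criterion and the follow-up waiver is on the page and must be reconciled. As written, undelivered attempts are outside both primary analyses. Aborted ITT cases without a recorded failure can leave the effectiveness denominator and, under the SAP wording, so can those with one. The favourable bias is on effectiveness.

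Its size cannot be known from the documents. Under the assumptions in step 3, five omitted failures reverse a result near the anticipated rate and one reverses a minimum pass. Fewer cases, or cases that would not all be failures, would matter less. The change should be made, but the finding does not show that the trial's conclusion would be wrong.

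**What to change.** - Use one enrollment point in Protocol 6.5, 6.6.2, 8 and 10.2 and in SAP 3.3, for example consent plus the decision to use Lava once access is established. Make screen failure possible only before that point.
- Set ITT to all enrolled subjects. Name those in whom Lava entered the vasculature as a separate treated set, and state whether DMSO priming counts.
- Reconcile 8.8 with ITT by keeping the 30-day contact, for data collection, in aborted cases. Protocol 8.5 already allows it by telephone.
- Align the SAP definition of Completed Cases with Protocol 6.6.3, including its early-failure clause.
- Report the number of enrolled, undelivered and aborted cases. Pre-specify a sensitivity analysis in which enrolled lesions that received no Lava are non-successes.
- Do not extend that analysis to lesions given partial Lava plus adjunctive devices. The footnote to Protocol 8.2 and the Clinical Success definition in Section 18 allow these to be successes.

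The cost is wording changes in both documents, a few more telephone calls, and slightly less favourable effectiveness rates.
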